The data from the study will be used to support future financial modeling and to provide baselines for programs to educate patients about clinical trials, diet, and lifestyle changes delivered electronically. Since there is no existing measure, an a-priori power analysis is not overly instructive, but based on an assumed normal distribution the study seeks to enroll no fewer than 400 participants to yield a minimum theoretical power of around 0.8 and may include up to a maximum of 1,000 patients.

The study will also produce data on the incidence and staging of NAFLD and NASH, as indicated by their FibroScan scores, and will track, in aggregate, their response to information about clinical trials and dietary support delivered through online resources. This data will not be informed by the patient record as no personally identifiable data will be collected.

The dataset will include demographic information and general ethnicity so aggregate subtotals of the various populations may be examined for additional insights to inform future investigations.

DATA COLLECTION:

Demographics:

After signing the consent form the research subjects will fill out a basic form to provide demographic information, including sex, age, and race/ethnicity. We will measure height and weight prior to CAP/FibroScan testing.

Metabolic Syndrome:

Subjects will use a form to check YES or NO for comorbid components of the metabolic syndrome that they may or may not have:

- Obesity/overweight
- Diabetes mellitus
- Hypertension
- Hypercholesterolemia
- Hypertriglyceridemia
- Gout or elevated uric acid

Other Health Conditions:

Subjects will use a form to check YES or NO for other health conditions they may or may not have:

- Heart disease
- Heart attack
- Arrhythmia
- Stroke
- Arthritis
- Osteopenia/osteoporosis
- Hypothyroidism
- Low Vitamin D
- Low testosterone
- Menopausal state
- Inflammatory bowel disease (ulcerative colitis or Crohn's disease)
- Cancer
 - Skin: melanoma
 - Skin: basal cell or squamous cell cancers
 - Other type of cancers: lymphoma; leukemia; head or neck; thyroid; brain; breast; lung; stomach; colon; liver; ovary; uterus; prostate; bone

Diet:

Subjects will fill out a form using a 5-point scale of the frequency of their average weekly dietary intake of specific food types: (A. 0 days, B. 1-2 days, C. 3-4 days, D. 5-6 days, E. 7 days per week)

- Proteins: eggs, cheese, beans, fish, chicken, turkey, beef, pork

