 - The discussion provided useful information about FDA-approved clinical trials of therapies.
 - The discussion of my liver health will help me obtain better health care for my liver.
- b. If you answered dissatisfied or very dissatisfied, please check all the reasons for your answer:
- I do not understand what the CAP-FibroScan measures.
 - I do not understand how much fat I have within my liver.
 - I am not sure if I have or do not have scarring (fibrosis) of my liver.
 - The results did not give me a better understanding of my liver health.
 - The discussion did provide useful information about FDA-approved clinical trials of therapies.
 - The discussion of my liver health is unlikely to help me obtain better health care for my liver.

SUNN STUDY

STATISTICAL ANALYSIS PLAN

PRIMARY OUTCOME MEASURE – DETERMINE THE INCIDENCE AND STAGING OF UNDIAGNOSED NAFLD AND NASH IN A HEALTH CONSCIOUS SELF SELECTED POPULATION AS MEASURED WITH A FIBROSCAN

The study will measure the incidence and severity of the fat content and liver stiffness in an at large, self selected population who do not, at the time of testing, have a diagnosis of NAFLD, NASH or other liver disease. This will measure the incidence of undiagnosed liver disease and the statistical distribution of the disease staging in this population.

A key secondary outcome measure will be the incidence and disease distribution as a function of ethnicity.

We will analyze data using a standard statistical software package, Stata® 12.1 (Stata Corp, College Station, TX). We will express continuous variables using the mean \pm standard deviation, and we will test the null-hypothesis using the Student t-test. We will compare categorical variables using contingency table analysis. For all statistical tests, we will define a two-sided p-value of ≤ 0.05 as statistically significant. We will perform multivariate analysis of all risk factors found to be statically significant ($p \leq 0.05$) using univariate analysis.

Data Analysis

We will record all data in a Microsoft Excel worksheet. We will sequentially number each participating subject. We will not record any identifying information (e.g., names, initials, DOB, SSN, insurance, EPIC MRNs) in the database. Thus, all data assessments will maintain the anonymity of all participating subjects.

1. The primary goal is to calculate the proportion of men and women that when tested have CAP-FibroScan evidence of:
 - No fat or liver stiffness

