 - No fat but evidence of liver stiffness
 - Fat without liver stiffness
 - Fat with liver stiffness
 - Stiffness values indicative of cirrhosis
 - Stiffness values indicative of fibrosis without cirrhosis

NOTE: no individual follow up or track will be done as not personally identifiable information will be captured or retained.

2. The secondary goal is to determine factors that are statistically significantly associated with the presence or absence of fat with or without increased liver stiffness.

We will analyze data using a standard statistical software package, Stata® 12.1 (Stata Corp, College Station, TX). We will express continuous variables using the mean ± standard deviation, and we will test the null-hypothesis using the Student t-test. We will compare categorical variables using contingency table analysis. For all statistical tests, we will define a two-sided p-value of ≤0.05 as statistically significant. We will perform multivariate analysis of all risk factors found to be statically significant (p ≤0.05) using univariate analysis.

This exploratory goal seeks to determine the degree of satisfaction of subjects who undergo a screening CAP-FibroScan free of charge.

We will calculate the frequency of answers for each of the five items reflecting subjects' likelihood of:

- recommending this test to a friend or family member.
- sharing their results with their doctor.
- consulting with a liver specialist.
- seeking information about FDA-approved clinical trials of therapies for non-alcoholic fatty liver disease.
-

We will not perform statistical analyses for these descriptive data.

Disease Staging

The disease staging to be analyzed will be based upon these breakpoints from the FibroScan test. The test scores will be translated into these staging ranges for analysis.

Transient Elastography (TE):

Disease	F0-F1	F2	F3	F4
NAFLD/NASH	≤ 7.0	≤ 7.5	≤ 10.0	≤ 14.0

Reference: Current Gastroenterology Reports. 2014; 16: 372

TE Interpretation: The subject's liver stiffness score in kPa units shows:

- **F0:** No liver fibrosis
- **F1-2:** Mild-Moderate liver fibrosis
- **F3:** Severe liver fibrosis
- **F4:** Cirrhosis

Controlled Attenuation Parameter:

Steatosis Grade	% Steatosis on Liver Biopsy	CAP Value
Mild (S1)	5-33%	225-275 dB/M
Moderate (S2) to Severe (S3)	>33% >66%	275-400 dB/M

Reference: World J Gastroenterol. 2016; 22: 7236

DATA COLLECTION

Demographics:

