The data for analysis will be captured by these patient completed forms to provide demographic information, including sex, age, and race/ethnicity. We will measure height and weight prior to CAP/FibroScan testing.

Metabolic Syndrome:

Subjects will use a form to check YES or NO for comorbid components of the metabolic syndrome that they may or may not have:

- Obesity/overweight
- Diabetes mellitus
- Hypertension
- Hypercholesterolemia
- Hypertriglyceridemia
- Gout or elevated uric acid

Other Health Conditions:

Subjects will use a form to check YES or NO for other health conditions they may or may not have:

- Heart disease
- Heart attack
- Arrhythmia
- Stroke
- Arthritis
- Osteopenia/osteoporosis
- Hypothyroidism
- Low Vitamin D
- Low testosterone
- Menopausal state
- Inflammatory bowel disease (ulcerative colitis or Crohn's disease)
- Cancer
 - Skin: melanoma
 - Skin: basal cell or squamous cell cancers

- Other type of cancers: lymphoma; leukemia; head or neck; thyroid; brain; breast; lung; stomach; colon; liver; ovary; uterus; prostate; bone

Diet:

Subjects will fill out a form using a 5-point scale of the frequency of their average weekly dietary intake of specific food types: (A. 0 days, B. 1-2 days, C. 3-4 days, D. 5-6 days, E. 7 days per week)

- Proteins: eggs, cheese, beans, fish, chicken, turkey, beef, pork
- Starchy carbohydrates: breads, rolls, pasta, cereals, potatoes, rice, corn, peas, lima beans
- Non-starchy vegetables: lettuces, kale, carrots, green beans, broccoli, peppers, onions, cucumber
- Fats: butter, margarine, avocado, oils (olive, safflower, cottonseed, peanut, sesame, walnut)
- Nuts: peanuts, walnuts, cashews, almonds, macadamias, peanuts
- Sugars or Syrups: sugar, high fructose corn syrup (sodas), maple or corn syrups
- Fast food meals
- Eating out at restaurants

Exercise:

Subjects will fill out a form using a 5-point scale of the frequency of their average weekly exercise:

- (A. 0 days, B. 1-2 days, C. 3-4 days, D. 5-6 days, E. 7 days per week)
- Cardiovascular: brisk walking, jogging, biking, treadmill, stationary bike, stair stepper, elliptical, swimming laps
 - Strength: weight lifting, resistance machines or cords

Alcohol:

Subjects will fill out a form quantifying their average weekly total of alcoholic drinks:

(1 drink= 12 oz. beer, 6 oz. wine, 1.5 oz. hard liquor; 3 oz. brandy, sherry, liqueur):

- None
- 1-2 drinks/week
- 3-4 drinks/week
- 5-6 drinks/week
- 7-8 drinks/week
- 9-10 drinks/week

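### Entry to the multivariable model depends solely on an unadjusted p≤0.05, so an offset factor or a needed confounder can be dropped from the secondary-goal analysis

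*Combined protocol and SAP*

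**What the plan says.** The SAP's Data Analysis section sets the aim: "The secondary goal is to determine factors that are statistically significantly associated with the presence or absence of fat", with or without increased stiffness. Continuous variables are compared by t-test ("we will test the null-hypothesis using the Student t-test") and categorical variables by contingency table. The threshold is common to all tests: "we will define a two-sided p-value of ≤0.05 as statistically significant". The paragraph closes with the entry rule, "We will perform multivariate analysis of all risk factors found to be statically significant" at that threshold in univariate analysis. The same paragraph stands under Primary Outcome Measure.

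No covariate is forced in. There is no looser entry threshold, no re-entry step and no sensitivity model, and neither the model type nor its outcome variable is named.

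The sample is described as "liver stiffness in an at large, self selected population". The Data Collection section provides sex, age, race/ethnicity, diabetes, body size ("We will measure height and weight prior to CAP/FibroScan testing") and alcohol ("Subjects will fill out a form quantifying their average weekly total of alcoholic drinks"). On sample size, Intended Use of the Data says "the study seeks to enroll no fewer than 400 participants", with a maximum of 1,000.

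**The concern.** An unadjusted p-value shows neither whether a factor has an association of its own nor whether it is needed as a confounder. Two errors can follow.

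1. A factor that raises risk, but is more common in people at lower risk for another reason, can look flat in the unadjusted table. It fails the screen and is never examined with the other reason held constant.
2. A real confounder that misses p≤0.05 is not in the model, so the factors that remain are not adjusted for it.

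At stake is the list of factors reported as associated after adjustment. Since the main candidate adjusters are collected anyway, their presence in the model need not depend on a test result.

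**Working it through.** **The plan's own figure.** Intended Use of the Data gives n=400 for power of around 0.8, with no effect size, rate or comparison. It cannot be reproduced. Solved backwards for an assumed 200 v 200, the detectable difference is (1.960+0.842)×√(2/200) = 0.28 SD. The present point does not depend on it.

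**Inputs.** From the documents: the entry rule, the two-sided 0.05 threshold, the unadjusted tests, and n=400 to 1,000. Assumed, because the documents give none: factor in 20% of the sample, independent odds ratio (OR) 1.8, BMI SD 4.5, BMI OR 1.8 per 5 units, outcome prevalence 30%, and modest effects of age, sex, ethnicity (4 groups), diabetes and alcohol that are independent of the factor.

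**Mechanism, by arithmetic.** With no BMI difference between carriers and others, the assumed model gives unadjusted prevalences of 39.5% v 27.7%:

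OR = (0.395/0.605)/(0.277/0.723) = 0.653/0.383 = 1.70.

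This is a little under 1.8 because an odds ratio averaged over other predictors moves towards 1. If carriers are 3 BMI units lower, the prevalences are 33.7% v 29.1%:

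OR = (0.337/0.663)/(0.291/0.709) = 0.508/0.410 = 1.24.

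The independent OR is 1.8 in both cases. The chance that the second case passes the screen at n=400 (80 carriers, 320 others) is:

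- pooled proportion 0.2×0.337+0.8×0.291 = 0.300
- SE under the null √(0.300×0.700×(1/80+1/320)) = 0.0573
- SE under the alternative √(0.337×0.663/80+0.291×0.709/320) = 0.0586
- Φ((0.046−1.96×0.0573)/0.0586) = Φ(−1.13) = 0.13

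At n=1,000 the two SEs are 0.0362 and 0.0371, giving Φ(−0.67) = 0.25.

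**Simulation.** There were 3,000 replicates per scenario (Monte Carlo SE at most 0.9 points). Detection under the screen means that the factor passes univariately and is then significant in the model of passing terms. The comparator keeps the six named covariates and the factor without screening.

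| BMI in carriers | n=400, screen v fixed | n=1,000, screen v fixed |
|---|---|---|
| 3 lower | 13.6 v 50.9% | 23.8 v 87.5% |
| 1 lower | 38.8 v 56.8% | 73.4 v 91.6% |
| no gap | 48.7 v 55.6% | 87.8 v 91.3% |
| 1 higher | 56.9 v 57.6% | 91.4 v 91.7% |
| 3 higher | 56.2 v 57.3% | 91.4 v 91.7% |

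The top row agrees with the hand calculation. For a gap of 1 unit lower, the loss is 56.8−38.8 = 18.0 points and 91.6−73.4 = 18.2 points. A separate run of that scenario gave 36 v 54% and 73 v 90%. Varying prevalence (10 to 50%), factor share (10 to 40%) and OR (1.4 to 2.5), the loss was −0.1 to 2.2 points with same-direction confounding, 0.2 to 7.7 with no gap, and 0.8 to 24.4 with carriers 1 unit lower.

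**Lost adjuster.** Take a binary confounder in 30% of the sample, outcome prevalence 30%. With OR 1.5 it fails the screen 57% of the time at n=400 and 21% at n=1,000; with OR 1.8, 30% and 2%. For the resulting bias, let a null factor be carried by 50% of those with the confounder and 20% of those without. With OR 1.5 the outcome risks are 36.1% and 27.4%. The confounder is present in 0.15/0.29 = 51.7% of carriers and 0.15/0.71 = 21.1% of others. Outcome prevalence is then 31.9% v 29.2%, a spurious OR of 1.13. At confounder OR 1.8 it is 1.20.

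**The case against.** The strongest reply is that every effect size above is assumed and that material loss needs opposing confounding, for which the documents give no evidence. That stands: the figures show what can happen, not what will. One feature of the design makes the opposing case less contrived. Eligibility requires at least one listed chronic condition, so someone without a given condition must qualify through another. Assume a listed factor in 10%, diabetes in 25% and any other listed condition in 40%, all independent before selection. Among eligible people, diabetes is then present in 25% of those with the factor but in 0.25/(1−0.75×0.60) = 45% of those without. If conditions cluster positively in the population, this weakens or reverses, so the direction remains open.

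Second, the secondary goal speaks of association, not of independent effects, and the SAP does not say that screened-out factors go unreported. That also stands. Univariate results answer part of the goal, and the point concerns only the adjusted part.

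Third, requiring two significant tests lowers false positives slightly, so part of the no-gap loss buys something. That is fair.

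A reader might infer that the screen undermines the prevalence findings or the choice of cohorts for screening. The documents do not support this. The primary proportions involve no model, and the protocol's cohort question rests on observed prevalence by condition, which the screen does not touch.

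**Conclusion.** The point holds as a minor one. The stated entry rule can remove a factor whose independent association is offset, and can remove a confounder that other factors need. The SAP does not say that this is the only route into the model, but it offers no other.

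The consequence is confined to adjusted associations under the secondary goal. Size and direction cannot be determined from the documents: about 18 points of detection in the assumed case of OR 1.8 with carriers 1 BMI unit lower, and essentially nothing when confounding runs with the effect. The bias from a lost adjuster is modest in the cases worked. A reader might take the 18 points, or the larger losses at a 3-unit gap, as the expected loss in this study. They are not, since they rest wholly on assumed inputs. Nor does reaching 1,000 participants reliably cure the problem: under the assumed opposing gaps of 1 and 3 units at 30% prevalence, the loss in points is as large or larger than at 400.

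**What to change.** In both places, replace the entry sentence with:

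> For each secondary-goal outcome (fat v no fat; fat with increased stiffness v all others) we will fit one logistic model that includes age, sex, BMI, ethnicity, diabetes and alcohol (ordered categories, with overlapping categories merged before analysis) regardless of univariate p-value, together with all other factors with univariate p≤0.05, mutually adjusted. Each remaining factor will then be added in turn to this full model and labelled exploratory. Adjusted odds ratios with 95% CI will be reported beside the unadjusted results for all factors. If events are too few for the total number of model parameters, by a limit fixed before analysis, the outcome will be reported descriptively.

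Joint adjustment matters. Adding every other factor to the six covariates one at a time looks simpler but gives up the mutual adjustment that the SAP already has. In simulation under assumed inputs, with a null factor tied to an unlisted confounder of OR 2.5, it raised false positives from 2.5 to 22% (n=400) and from 4 to 45% (n=1,000) relative to the SAP's rule. It also failed to recover a true factor offset by such a confounder.

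Merging is needed because the alcohol form overlaps at 10 drinks (9-10 and 10-12) and at 14 (13-14 and 14-20).

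The cost is wording, a few degrees of freedom, and possibly no model for a rare outcome. With an assumed 4 ethnicity groups and alcohol as a single score, the fixed covariates take 1+1+1+3+1+1 = 8 parameters. At an illustrative 10 events each, that is 80 events: 80/400 = 20% prevalence, or 80/1,000 = 8%, and more once other factors enter. An unlisted confounder that misses the screen still goes unadjusted in the main model. BMI may lie on the pathway from ethnicity to liver fat, so unadjusted prevalence by ethnicity should stay the main descriptive result.

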- Starchy carbohydrates: breads, rolls, pasta, cereals, potatoes, rice, corn, peas, lima beans
- Non-starchy vegetables: lettuces, kale, carrots, green beans, broccoli, peppers, onions, cucumber
- Fats: butter, margarine, avocado, oils (olive, safflower, cottonseed, peanut, sesame, walnut)
- Nuts: peanuts, walnuts, cashews, almonds, macadamias, peanuts
- Sugars or Syrups: sugar, high fructose corn syrup (sodas), maple or corn syrups
- Fast food meals
- Eating out at restaurants

Exercise:

Subjects will fill out a form using a 5-point scale of the frequency of their average weekly exercise:

(A. 0 days, B. 1-2 days, C. 3-4 days, D. 5-6 days, E. 7 days per week) ○ Cardiovascular: brisk walking, jogging, biking, treadmill, stationary bike, stair stepper, elliptical, swimming laps ○ Strength: weight lifting, resistance machines or cords

Alcohol:

Subjects will fill out a form quantifying their average weekly total of alcoholic drinks:

(1 drink= 12 oz. beer, 6 oz. wine, 1.5 oz. hard liquor; 3 oz. brandy, sherry, liqueur):

- None
- 1-2 drinks/week
- 3-4 drinks/week
- 5-6 drinks/week
- 7-8 drinks/week
- 9-10 drinks/week
- 10-12 drinks/week
- 13-14 drinks/week
- 14-20 drinks/week
- 21 or more drinks/week

Other Liver Diseases:

Subjects will check YES or NO for other liver-related diseases that they may or may not have:

- Hepatitis B alone
- Hepatitis B with Hepatitis D
- Hepatitis C
- Hepatitis E
- Autoimmune hepatitis
- Primary biliary cholangitis
- Primary sclerosing cholangitis
- Iron overload
- Alpha-1-antitrypsin deficiency

Reporting of CAP-FibroScan Results to Participating Subjects:

A trained individual will perform the CAP-FibroScan according to the FDA-approved, manufacturer's protocol. A licensed hepatologist will determine the degree of fibrosis and will review the results and the steatosis based on the values in the following tables:

Transient Elastography (TE):

Disease	F0-F1	F2	F3	F4
NAFLD/NASH	≤ 7.0	≤ 7.5	≤ 10.0	≤ 14.0

Reference: Current Gastroenterology Reports. 2014; 16: 372

TE Interpretation: The subject's liver stiffness score in kPa units shows:

- **F0:** No liver fibrosis
- **F1-2:** Mild-Moderate liver fibrosis
- **F3:** Severe liver fibrosis
- **F4:** Cirrhosis

Controlled Attenuation Parameter:

Steatosis Grade	% Steatosis on Liver Biopsy	CAP Value
Mild (S1)	5-33%	225-275 dB/M
Moderate (S2) to Severe (S3)	>33% >66%	275-400 dB/M

Reference: World J Gastroenterol. 2016; 22: 7236

CAP-FibroScan Experience and Satisfaction Survey:

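### The binding stiffness staging table prints only upper limits: readings above 14.0 kPa have no stage, the start of F4 is unclear, and the primary cirrhosis proportion is not fixed by the plan

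*Combined protocol and SAP*

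**What the plan says.** The SAP's Disease Staging section states that "The disease staging to be analyzed will be based upon these breakpoints from the FibroScan test" and that "The test scores will be translated into these staging ranges for analysis". The table that follows has one row (NAFLD/NASH) and four cells, all with the same sign:

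| Stage | F0-F1 | F2 | F3 | F4 |
|---|---|---|---|---|
| kPa | ≤ 7.0 | ≤ 7.5 | ≤ 10.0 | ≤ 14.0 |

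The key beneath it gives labels without numbers: F0 is no fibrosis, F1-2 is "Mild-Moderate liver fibrosis", F3 is severe fibrosis and F4 is cirrhosis.

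The protocol prints the same table and key under Reporting of CAP-FibroScan Results to Participating Subjects. There, "A licensed hepatologist will determine the degree of fibrosis", but from those same values, so this step adds no separate cut-off.

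The SAP's primary goal (Data Analysis, item 1) is a list of six proportions. Two of them are "Stiffness values indicative of cirrhosis" and "Stiffness values indicative of fibrosis without cirrhosis", and neither has a kPa value. The Primary Outcome Measure section also promises "the statistical distribution of the disease staging in this population". The protocol's Intended Use of the Data says: "The study will also produce data on the incidence and staging of NAFLD and NASH".

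**The concern.** F4 is the top stage, so a table that closes it at 14.0 kPa gives the stiffest livers no stage and drops them from the cirrhosis count. An analyst would probably notice this and depart from the table, but the plan does not say how. Two repairs suggest themselves:

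- **(a)** Keep the upper limits and open the top, so that F4 is everything above 10.0.
- **(b)** Treat the F2, F3 and F4 figures as lower bounds, so that F4 starts at 14.0.

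Someone reading 12 kPa is cirrhotic under (a) and F3 under (b).

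A second defect affects the lower edge of fibrosis without cirrhosis. By the columns it starts at F2, since F1 is merged with F0. By the key it starts at F1, and no printed value separates F0 from F1.

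The result is meant to support a change in screening guidance. If the repair is chosen after the readings are in, the primary cirrhosis proportion is chosen with it.

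**Working it through.** **Inputs from the documents.** Limits 7.0, 7.5, 10.0 and 14.0 kPa (SAP Disease Staging; the same in the protocol). Minimum enrolment 400 (protocol, Intended Use of the Data), used here only for scale. No sample-size or power figure in the plan depends on the table, so there is none to reproduce.

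**Step 1: pass readings through the table.** Read cell by cell, the table does not separate stages at all: 5 kPa satisfies all four cells. The closest workable reading is successive upper limits, called the printed bands below.

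| Reading (kPa) | Printed bands | Repair (a) | Repair (b) |
|---|---|---|---|
| 7.0 | F0-F1 | F0-F1 | F0-F1 |
| 7.2 | F2 | F2 | none |
| 8 | F3 | F3 | F2 |
| 12 | F4 | F4 | F3 |
| 14.0 | F4 | F4 | F4 |
| 14.1, 20, 40 | none | F4 | F4 |

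The F4 groups under the printed bands and under (b) share only the value 14.0. This step needs no distribution.

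**Step 2: illustrate the size.** The documents give no stiffness distribution. I assume stiffness is log-normal with median m and SD of log s, so that P(X ≤ x) = Φ(ln(x/m)/s), and multiply by 400.

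Mid-case, m = 5.5 and s = 0.40:

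- P(X > 10.0): z = ln(10/5.5)/0.40 = 1.495, giving 0.0675, or 27.0 people.
- P(X > 14.0): z = ln(14/5.5)/0.40 = 2.336, giving 0.0098, or 3.9 people.
- Cirrhosis: printed bands 27.0 − 3.9 = 23.1 (5.8%); (a) 27.0 (6.8%); (b) 3.9 (1.0%).
- F2-F3: printed bands or (a), above 7.0 to 10.0, 400 × (0.9325 − 0.7267) = 82.3; (b), 7.5 to below 14.0, 400 × (0.9902 − 0.7809) = 83.7.

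Over the grid m = 5.0, 5.5, 6.0 by s = 0.35, 0.40, 0.45, 0.50:

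| Expected count of 400 | Minimum | Maximum |
|---|---|---|
| F4, printed bands (above 10.0 to 14.0) | 8.9 | 43.4 |
| F4, repair (a) (above 10.0) | 9.5 | 61.4 |
| F4, repair (b) (14.0 and over) | 0.65 | 18.0 |
| No stage, printed bands (above 14.0) | 0.65 | 18.0 |
| No stage, repair (b) (between 7.0 and 7.5) | 16.7 | 27.2 |
| F2-F3, printed bands or (a) | 57.7 | 103.0 |
| F2-F3, repair (b) | 48.7 | 113.0 |

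Ratio of the cirrhosis proportions, (a) to (b): 61.4/18.0 = 3.4 at (6.0, 0.50) and 9.53/0.653 = 14.6 at (5.0, 0.35).

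For F2-F3 the fair comparison is within one distribution. There, (b) minus the printed bands runs from about −9 to +23 of 400.

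**Step 3: the F1 boundary.** If F1 counts as fibrosis, as the key has it, the fibrosis-without-cirrhosis count cannot be computed, because no kPa value divides the F0-F1 column.

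**The case against.** Six points deserve weight.

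- **A misread sign.** The text was read from PDF by a program, and two copies read the same way are weak confirmation. If the original has ≥ for F2 to F4, the gap above 14.0 and the doubt about F4 disappear. The original page should be checked. Even then, readings between 7.0 and 7.5 would have no stage and the key would still conflict with the columns.
- **The repairs are not equally close to the text.** Once the cells are read as successive limits, (a) changes one of them, while (b) reverses three signs and opens a gap. That favours (a) as a reading of the page. It does not show which limits the sponsor intended, and the plan is silent.
- **The multiple depends on the assumption.** This stands. At SD of log 0.55 the smallest ratio is 2.9, and at 0.70 it is about 2.1 to 2.3. The high end comes from a corner where (b) expects fewer than one person in 400.
- **Fibrosis without cirrhosis moves much less.** This also stands for F2-F3: the mid-case difference is 1.4 people. The people classified differ, but the proportion may barely change.
- **The columns could simply govern.** Only they carry numbers, so fibrosis would start at F2. That is reasonable, but the plan should say so, because its own key says otherwise.
- **Harm is limited.** The outcome is descriptive, and test data are kept for at least 5 years (protocol, Data Management), so restaging is possible. That makes correction cheap, but it does not supply a prespecified rule.

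**Conclusion.** The concern holds, and the table must be fixed before analysis. As written, the rule removes readings above 14.0 kPa from the cirrhosis count. No other part of the documents gives a kPa limit that would settle whether F4 starts above 10.0 or at 14.0. The primary cirrhosis proportion is therefore undetermined. Fibrosis without cirrhosis is undetermined too, chiefly through the conflict over F1.

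These conclusions rest on the printed table alone, subject to confirming the signs on the original page. The size rests on an assumed log-normal distribution: several-fold for cirrhosis over the main grid, about two-fold if the spread is much wider, and modest for F2-F3. The four fat-by-stiffness categories are not at issue: they can be computed with the 7.0 kPa break once the SAP names that as the rule.

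**What to change.** Before any staging is run:

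1. Check the signs on the original page and reconcile the table with its cited reference and its key, in both the SAP and the protocol. Every reading should fall in exactly one stage: contiguous, non-overlapping intervals with an open-ended top stage. The cut-offs are for the sponsor to confirm, and none is proposed here.
2. Make the key use the same stage groups as the columns.
3. Add a sentence to the SAP's Data Analysis section saying which stages count as liver stiffness, as fibrosis without cirrhosis and as cirrhosis.

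The cost is one table and its key corrected in two places, plus one mapping sentence. No new data are needed.

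### The risk-factor analysis has only staged outcomes; adding CAP and log stiffness as continuous outcomes is a cheap improvement that can recover power

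*Combined protocol and SAP*

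**What the plan says.** In the SAP, under Disease Staging, the plan for the readings is: "The test scores will be translated into these staging ranges for analysis". The tables there give bands for stiffness in kPa and for CAP in dB/m. No exception is made for any analysis.

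Under Data Analysis, item 1 (the primary goal) is a set of proportions. Item 2 holds the secondary goal, in these words: "determine factors that are statistically significantly associated with the presence or absence of fat with or without increased liver stiffness". The key secondary outcome, under Primary Outcome Measure, is incidence and disease distribution by ethnicity, which is again categorical.

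Two general sentences cover testing. For categorical data: "We will compare categorical variables using contingency table analysis". For continuous data: "We will express continuous variables using the mean ± standard deviation, and we will test the null-hypothesis using the Student t-test". The second does not say which variables it covers. The threshold is common to all: "we will define a two-sided p-value of ≤0.05 as statistically significant". Factors that pass it in univariate analysis go forward to the multivariate analysis.

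**The concern.** The device returns numbers on continuous scales, and a yes/no version is needed only where a proportion is the target. When the question is which factors go with fat or stiffness, a cut-off treats a reading just above the band edge like one far above it. If a factor moves readings generally, much of that movement never crosses the edge and is not counted.

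Two things are at stake. A real association may be missed at the univariate step. Because that step also decides entry to the multivariate analysis, a factor missed there is lost from the adjusted results too.

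**Working it through.** **Inputs.** From the documents: at least 400 and at most 1,000 participants and power of about 0.8 (protocol, Intended Use of the Data); two-sided 0.05 (SAP). The documents give no effect size, standard deviation, group split or expected prevalence, so these are assumed below.

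**1. The plan's own figure.** The protocol says "the study seeks to enroll no fewer than 400 participants to yield a minimum theoretical power of around 0.8". Without an effect size this can only be solved backwards: d = (1.960 + 0.842) × √(1/n₁ + 1/n₂).
- Groups of 200 and 200: 2.802 × 0.100 = 0.28 SD.
- Groups of 120 and 280: 2.802 × 0.109 = 0.31 SD.

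Other inputs fit as well (10% against 20% needs 398), so the figure is neither confirmed nor refuted. I use 0.28 SD as the effect that a continuous reading detects with 80% power at 400.

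**2. A yes/no split when the factor shifts everyone.** With a normal reading and a share p above the cut, efficiency relative to the continuous reading is E = φ(z)² / [p(1 − p)], where z is the normal quantile with p above it. At p = 20%: 0.2800² / (0.2 × 0.8) = 0.0784 / 0.16 = 0.490. For power, the two group shares are the normal tail areas beyond z + 0.14 and z − 0.14 (16.3% and 24.1% at p = 20%).

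| p | φ(z) | E | Information lost | 400 act like | Power at 400, 0.28 SD | Total N for 80% |
|---|---|---|---|---|---|---|
| 50% | 0.3989 | 0.637 | 36% | 255 | 0.61 | 632 |
| 20% | 0.2800 | 0.490 | 51% | 196 | 0.50 | 824 |
| 10% | 0.1755 | 0.342 | 66% | 137 | 0.37 | 1,186 |
| 5% | 0.1031 | 0.224 | 78% | 90 | 0.26 | 1,822 |
| 3% | 0.0680 | 0.159 | 84% | 64 | 0.20 | 2,574 |

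The formula is symmetric in p and 1 − p. The 36% is the smallest loss that a two-way split can have (1 − 2/π). There is no matching ceiling: at 1% the loss is 93%. At 10% and below, the total needed exceeds the maximum of 1,000.

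**3. Skewness.** Simulation with a log-normal reading (log-SD 0.4, shift 0.28 SD, N = 400) gave t-test power of about 0.79 on the log scale and 0.76 on the raw scale. The split gave 0.61, 0.51, 0.36, 0.25 and 0.20 at 50, 20, 10, 5 and 3%. The pattern survives.

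**4. Ordered stages instead of yes/no.** Here E = Σ (φ_lower − φ_upper)² / p_j over the stages. For three equal grades the cuts lie at ±0.431, where φ = 0.3636, so E = 2 × 0.3636² × 3 = 0.793 and the loss is 21%. Shares of 50/25/25 lose 25%, and 60/20/20 lose 30%. Illustrative stiffness stages of 80/3/10/7% lose 48%, and 90/2/5/3% lose 65%. These figures hold only if the test uses the order of the stages, which the SAP does not specify.

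**5. A factor that raises the share of diseased livers.** Assume N = 400 with the factor present in 30%, healthy readings N(0,1), diseased readings 2.5 SD higher, a cut at 2 SD, and 15% diseased with the factor against 5% without. The expected shares above the cut are 0.85 × 0.0228 + 0.15 × 0.691 = 12.3%, and 0.95 × 0.0228 + 0.05 × 0.691 = 5.6%. Simulated power was about 43% on the continuous reading and 62 to 64% on the cut. With 12% against 3% diseased it was 37% and 63%. With diseased readings 3 SD higher and 15% against 5% it was 49% and 73%. Here the ordering reverses.

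**The case against.** The strongest reply is that the staged outcome is what the study wants to know. The protocol asks which groups would justify screening, and a difference in mean kPa within the normal range does not answer that. Item 2 is a joint fat-by-stiffness classification, which two separate regressions do not reproduce. This stands, and it rules out replacing the staged outcomes.

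Step 5 also stands: which analysis has more power depends on how a factor acts, and the documents do not settle that.

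Four stronger readings are tempting, and the documents do not support them.
- **A fixed loss, such as a third to five sixths.** That range needs a normal shift, a two-way split and prevalences from about 50% down to 3.2%. None of these is in the documents. The 3% row in particular has no named contrast in item 2; cirrhosis is listed only among the primary proportions.
- **Information already collected is thrown away.** The SAP records all data and the protocol stores the scan results. The loss is in the planned analysis only.
- **Continuous analysis is excluded.** The Student t-test sentence could cover CAP and kPa. With a fat/no-fat outcome it more naturally covers predictors such as age and weight. The SAP is unclear on this, and the specific staging sentence points the other way.
- **Staging brings no benefit.** Step 5 shows a case where it does.

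**Conclusion.** This is a cheap improvement, not an error that undermines the study. The SAP names no continuous outcome for the risk-factor goal. Under a common shift in a normal reading, a yes/no split loses about 36% of the information at 50% prevalence, 51% at 20%, 66% at 10% and 84% at 3%. An effect with 80% power on the reading then has between 0.61 and 0.20. Those sizes rest on assumed prevalences and on that one mechanism. Ordered stages can lose less, and the comparison can favour the cut when a factor mainly adds clearly diseased livers. Since the mechanism is unknown in advance, running both analyses is better protection than choosing either. The primary proportions are not affected.

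**What to change.** Amend the SAP as follows.
- Keep the staged proportions for the primary goal, and the staged outcome for the ethnicity comparison and for item 2.
- Add to item 2 pre-specified linear regressions of CAP (dB/m) and log(kPa), as two separate outcomes with robust standard errors, both univariate and multivariable.
- State in advance which factors enter the continuous multivariable models, so that none is dropped solely because it missed p ≤ 0.05 on the yes/no outcome.
- Say which variables the Student t-test sentence covers, and confirm that the worksheet holds the numerical kPa and dB/m readings as well as the stages.
- Optionally, add the same continuous comparison for ethnicity, labelled supportive.

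The cost is SAP wording and analysis time; no new data or visits are needed. The downsides are two further outcomes tested per factor, and effects in dB/m or percent change in kPa that must be read beside the staged results.
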